September 10, 2019

US Department of Health and Human Services
[name]
[name]

PRINCIPAL INVESTIGATOR : [name]
TITLE : TrueTear in Sjogren's Disease Patients
PROTOCOL # : 830076

The following document spells out the study protocol and statistical analysis plan for this trial.

Sincerely,

[name]
Research Coordinator

Protocol

In this trial, the protocol is straightforward. The study consists of two visit days for the patient. The first day is considered the screening day. On the first day, a baseline Schirmer's test is performed after the patient's eyes have been anesthetized. The duration of this test is five minutes. At the end of the five minutes, the tear production is measured using the Schirmer strips. The patient must produce ten millimeters or less in at least one eye to qualify for the study. Next, the TrueTear device is simulated using two cotton swabs. One cotton swab is inserted into each nostril. Using Schirmer strips to measure tear production, the patient swirls the cotton swabs around in their nostrils until they produce four millimeters above their baseline in at least one eye. The patient is then to hold the cotton swabs in their nose for the remainder of the five minutes. In order to qualify for the study, the patient must produce four millimeters or greater in the study eye. In instances where the patient is of child-bearing age, a pregnancy test is performed to ensure that the patient is not pregnant.

After visit one, visit two can be completed the following day or any day during the next forty-five days. During visit two, the effectiveness of the device is tested. The patient is randomized to which application method, internal or external, is used first. During both the first and second applications, Schirmer strips are used to measure tear production over the course of five minutes. For the first three minutes, the device is used. For the remaining two minutes, the device is removed. Between the first and second applications, there must be a waiting period of at least forty-five minutes. This break ensures that the patient's tear glands have enough time to restore. This is necessary for accurate measurement of the effectiveness of the device.

Statistical Analysis Plan

Our plan to analyze the data from this trial will involve a few different comparisons, as well as factoring in a few different variables. First, we will look to compare both the internal and external stimulation results to the baseline results. When making these comparisons, the order in which application method was used first will be factored in. This will help us determine whether or not the order of application methods impacts the final results. Next, we will examine each stimulation method (cotton swabs, internal application with TrueTear device, and external application with TrueTear device) relative to baseline to see if the changes are statistically significant from baseline, and to determine an estimated mean change. We also plan to compare each application method to each other to determine if there is a statistically significant difference. While making the comparison, we also want to separately account for two different factors, patients on Sjogren's medication vs. patients not on Sjogren's medication and patients with a baseline Schirmer of less than 5 mm. vs. patients with a baseline Schirmer of greater than or equal to 5 mm. In a similar fashion, we also want to examine each application method individually to determine the p-value, confidence interval, mean, and standard deviation.

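### Does naming anesthetic only for the baseline Schirmer test bias the change-from-baseline comparisons?

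*Combined protocol and SAP*

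**What the plan says.** The document is a short combined protocol and analysis plan. In the Protocol section, the screening-day baseline Schirmer test is done under anesthetic: "eyes have been anesthetized. The duration of this test is five minutes". This is the only mention of anesthetic.

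The swab test comes next at the same visit. It uses Schirmer strips, and the patient stimulates the nostrils "until they produce four millimeters above their baseline in at least one eye". Nothing is said about the condition of the eyes.

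The device is tested at a separate visit: "After visit one, visit two can be completed the following day or any day during the next forty-five days". The measurement there is described in one sentence covering both methods: "During both the first and second applications, Schirmer strips are used to measure tear production over the course of five minutes". Again the anesthetic condition is not given. No unstimulated or sham reading is described for that day.

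The Statistical Analysis Plan section opens with the comparison against baseline: "First, we will look to compare both the internal and external stimulation results to the baseline results". It goes on to test and estimate the change from baseline for swabs, internal and external application, and then adds: "We also plan to compare each application method to each other to determine if there is a statistically significant difference".

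**The concern.** A change from baseline is interpretable only if the two readings differ in the stimulation and in nothing else that moves the measurement. Here the condition of one side is stated and that of the other is not. A reader who takes the text literally could picture an anesthetized baseline set against unanesthetized device readings on another day.

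If the strip itself provokes tearing and anesthetic suppresses it (an assumption, since the document does not say so), the device contrasts would combine two things: the effect of the device and the return of strip-provoked tearing. An inert device could then appear to work. A larger sample would not help, because the bias stays fixed while the standard error shrinks. Adjusting for application order would not help either, because order concerns the two visit-two applications and not the gap between visits. With no unstimulated reading at visit two, the data could not separate the two components afterwards. The first comparison in the analysis plan would be the one affected.

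**Working it through.** The document gives no sample size, standard deviation, significance level or effect size, so there is no figure to reproduce. The check has three parts.

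**1. What the text fixes**

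| Reading | Visit | Anesthetic condition |
|---|---|---|
| Baseline | one | anesthetized |
| Cotton swab | one, directly after baseline | not stated |
| Internal device | two, 1 to 45 days later | not stated |
| External device | two, same session as internal | not stated |

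No row says unanesthetized. Three of the four are silent.

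**2. Which contrasts could be affected**

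Let D be the true mean effect of a method, and R the mean shift in a reading caused by any difference in condition from baseline. R = 0 if conditions match.

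- Internal or external minus baseline: expected value D + R. The bias is R at any sample size.
- Internal minus external: (D_int + R) − (D_ext + R) = D_int − D_ext. The shift cancels if both applications are measured alike, and the protocol describes them in a single sentence.
- Device minus swab: (D_dev + R) − (D_swab + R_swab). The shift cancels if R_swab = R. Whether it does is not stated.

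The exposure is therefore the two device-versus-baseline contrasts, the swab-versus-baseline contrast if the swab reading differed from baseline, and possibly device versus swab.

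**3. Can the size be judged?**

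For an inert device (D = 0), a two-sided 5% paired t-test rejects with a probability given by the noncentral t distribution on n − 1 degrees of freedom, with noncentrality R√n/SD. All three inputs must be assumed.

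- R = 0: 5%, at any n and SD.
- R = 2 mm, SD = 5 mm, n = 20: noncentrality 2 × √20 / 5 = 1.79, rejection 40%.
- R = 0.5 mm, SD = 8 mm, n = 20: rejection 6%.
- R = 3 mm, SD = 3 mm, n = 20: rejection 99%.

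Over R from 0.5 to 3 mm and SD from 3 to 8 mm, the range runs from about 5% (the low end at n = 10) to over 99% (the high end at n = 40). An interval that wide says only that a paired test detects a non-zero shift. It gives no evidence that a shift exists here. The one firm result is that the mean change would be biased by exactly R, with R unknown and possibly zero.

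**The case for a change.** The strongest case for acting is that the reader cannot tell which situation applies. Visit two is on another day, so anesthetic given at visit one cannot be assumed to persist. The authors plainly care about measurement conditions, since they impose a break of at least forty-five minutes between applications for the sake of accurate measurement. Against that background, leaving the anesthetic condition of the same readings unwritten looks like an oversight, and one sentence would settle it.

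Much of this stands. The ambiguity is real, and a mismatch, had there been one, could not be repaired from these data.

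It does not show that the plan, as written, leads to a wrong analysis. The protocol describes the Schirmer method once and then refers to the strips in short form, as a two-paragraph summary would. The swab test follows directly and is scored as an increment over the baseline, which presupposes comparable readings. Carrying the method forward is a natural reading. Reading the later tests as unanesthetized adds something the text does not say. Both the mechanism and its size, in patients who must have a baseline of 10 mm or less in at least one eye, come from outside the document.

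The lack of an unstimulated reading at visit two is a separate design question. It would remain with perfectly matched anesthetic, so it does not strengthen this point.

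**Conclusion.** The concern does not call for a change. The document leaves a procedural detail unwritten. It does not state a mismatch. If the baseline method is carried through, which is a sensible reading, the offset is zero and the planned comparisons are unaffected by this point.

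The conclusion rests on two things: the text neither requires nor excludes anesthetic for the later readings, and both visit-two applications are measured in the same way. If the condition at visit two did in fact differ from baseline, the internal- and external-versus-baseline mean changes would carry an unknown offset R, and the change could not be attributed wholly to the device. That would be a matter for interpretation when results are reported, where the condition actually used is known. The randomized-order comparison of internal with external application would still hold.

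### The 4 mm swab threshold has two unreconciled wordings and an undefined study eye, and the SAP tests for significance the swab reading that decides enrollment

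*Combined protocol and SAP*

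**What the plan says.** The Protocol's account of visit one contains three statements about eyes and millimeters, in this order:

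- Baseline criterion: "The patient must produce ten millimeters or less in at least one eye to qualify for the study".
- Swab procedure: the patient swirls the swabs "until they produce four millimeters above their baseline in at least one eye". Then: "The patient is then to hold the cotton swabs in their nose for the remainder of the five minutes".
- Swab criterion: "In order to qualify for the study, the patient must produce four millimeters or greater in the study eye".

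The last sentence is the only place where a study eye is mentioned. Visit two, as described, has the internal and external device applications in randomized order and no swab.

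The Statistical Analysis Plan says "we will examine each stimulation method (cotton swabs, internal application with TrueTear device, and external application with TrueTear device) relative to baseline", and gives the purpose as "to see if the changes are statistically significant from baseline, and to determine an estimated mean change". When it turns to comparing application methods with each other, it adds: "While making the comparison, we also want to separately account for two different factors". One of these factors is "patients with a baseline Schirmer of less than 5 mm. vs. patients with a baseline Schirmer of greater than or equal to 5 mm". It names neither the eye to be analyzed nor an analysis set.

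**The concern.** Two matters are linked.

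First, the entry rule cannot be read one way only. The swirl target is relative to baseline and can be met in either eye. The qualifying sentence has no baseline in it and refers to one particular, unidentified eye. The low-baseline eye, the responding eye and the analyzed eye could therefore differ within one patient. A reader cannot tell who was eligible, or which eye the results and the baseline subgroups describe.

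Second, the SAP treats the swab as a third stimulation method whose change from baseline is to be tested. The only swab reading described is the one that decides whether the patient enters, and it is taken while the patient stimulates until a target is reached. A small p-value could then be read as evidence that the swab works when selection has produced at least part of it.

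**Working it through.** **Inputs.** From the Protocol: baseline of 10 mm or less in at least one eye; a 4 mm rise in at least one eye; 4 mm or more in the study eye. From the SAP: a significance test and a mean change for the swab. The documents give no sample size, significance level, standard deviation or effect size, so there is no planned figure to reproduce.

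**1. The two thresholds in a single eye.** For baseline b, a rise rule needs a swab reading of at least b + 4. The literal qualifying sentence needs at least 4.

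| Baseline (mm) | Rise rule needs (mm) | Literal sentence needs (mm) |
|---|---|---|
| 0 | 4 | 4 |
| 5 | 9 | 4 |
| 10 | 14 | 4 |

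Within one eye they agree for every reading only at b = 0. From b = 4 upward, the literal sentence is met with a change of zero. Because different eyes are named, the sentences can disagree even at 0 mm. Suppose both eyes start at 0 and the study eye reaches 3 while the other reaches 4: the swirl target is met and the qualifying sentence is not.

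**2. The choice of eye.** Take an invented patient with baselines of 3 and 8 mm and swab readings of 5 and 12 mm. Both written sentences are met whichever eye is the study eye (the second eye rises by 12 − 8 = 4; both swab readings are at least 4). The analyzed data still depend on the choice:

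- First eye: change 5 − 3 = +2 mm, baseline group under 5.
- Second eye: change +4 mm, baseline group 5 or more.

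If the qualifying sentence is shorthand for a rise in the study eye, this patient also fails entry on the first eye and passes on the second.

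**3. The limiting case for the swab test.** Assume that enrolled patients are analyzed and that entry requires a 4 mm rise in the analyzed eye. Every swab change is then at least 4 mm, so the mean cannot be below 4 mm. With n positive changes out of n, the exact two-sided sign test gives p = 2 × 0.5ⁿ:

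- n = 5: 0.0625
- n = 6: 0.031
- n = 10: 0.002

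These values hold whatever the true swab effect. The SAP names no test; the sign test is used here because its result then depends on n alone.

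**4. Other readings of the rule.** An absolute rule removes readings below 4 mm. That forces a rise of at least 4 − b at baselines of 0 to 3 mm and forces none from 4 mm up. An either-eye rule forces a rise only in the eye that met it. Both push the mean change up and the p-value down without guaranteeing a positive result.

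**5. Illustration only.** A simulation with no swab effect used assumed values throughout: mean level 4 or 6 mm, between-patient SD 4 mm, reading SD 2 to 4 mm, between-eye correlation 0.7, lower-baseline eye analyzed, 20 patients, paired t-test at two-sided 0.05 with upper-tail rejections counted.

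| Selection on the swab | Mean change (mm) | Rejections |
|---|---|---|
| None (baseline cap and lower-eye choice only) | 0.7 to 2.1 | 25% to 51% |
| Absolute, study eye | 1.6 to 4.3 | 78% to 99.8% |
| Rise, either eye | 3.6 to 5.5 | about 100% |
| Rise, study eye | 4.9 to 6.9 | 100% |

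A one-eye truncated-normal calculation points the same way. Inflation is s·φ(a)/(1 − Φ(a)) with a = (c − μ)/s, where μ and s are the assumed mean and SD of the change and c is the smallest change admitted. For a rise rule (c = 4) with s of 2 to 4 mm, it is 1.6 to 3.2 mm at μ = 4 and 0.1 to 1.2 mm at μ = 8. For an absolute rule at b = 5 (c = −1) and μ = 4, it is 0.04 to 0.8 mm. Neither model includes swirling until the target is met, and both treat all the variation that is selected on as reading error.

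**The case against.** The strongest reply is that the qualifying sentence is loose drafting. It comes shortly after the swirl target, repeats the same number for the same test, and read literally would make the swab step pointless for a study eye already at 4 mm or more. Shorthand may well be what was meant. That weakens any claim that non-responders are deliberately admitted, but it does not remove the conflict between at least one eye and the study eye, and nothing defines the latter. The first sentence could equally be only a procedural step, with the reading after the hold as the criterion.

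On the analysis, three objections carry weight. The SAP names no analysis set; if all screened patients were analyzed, selection at entry would not apply, although stimulation would still be continued toward the target. If patients truly differ in response, a higher mean among enrolled responders is correct for that group, and only the reading-error part is bias. And because stimulation is adjusted to the response, an ordinary model of a change with a fixed true mean does not describe the procedure. These objections rule out firm millimeter figures. They do not rescue a significance test on a reading that decides entry, and the SAP attaches no caveat to it.

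It is also fair that the swab only simulates the device at screening, and that device effectiveness is tested at visit two. That limits the consequence.

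**Conclusion.** The point holds in limited form. The undefined study eye is the firmest part. The two wordings are unreconciled, whichever was intended. The planned swab test uses the reading that selects patients, so its p-value would come at least partly from selection if enrolled patients are analyzed.

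Three stronger conclusions might be inferred, and the documents support none of them:

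- **That the swab test must come out positive.** This follows only if enrolled patients are analyzed, the rule is a rise in the analyzed eye, and there are enough patients (six or more for a sign test at an assumed two-sided 0.05).
- **That the bias has a known size.** It depends on the rule, the eye, the spread of readings and the true response, none of which is given. The share of patients affected cannot be computed either.
- **That the device comparison fails.** The internal-external contrast is within patient, in randomized order, and uses visit-two readings that play no part in entry. It is not invalidated, and that contrast is where the SAP places the 5 mm split, although the split still needs a defined eye. Any swab-versus-device comparison is different, because only the swab reading was selected on.

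**What to change.** - Reconcile the two visit-one sentences into one entry rule that says whether 4 mm is a change from that eye's baseline or an absolute reading, and in which eye. No view is taken here on which is right.
- Define the study eye in advance by a fixed rule that does not use the swab response and, ideally, does not pick the lower baseline reading. Choosing the lower-baseline eye adds regression to the mean to every comparison with baseline, including those for the device. Use the defined eye for all analyses and for the 5 mm split.
- State the analysis set.
- Report the swab-versus-baseline result as descriptive, without a significance claim, or state beside it that enrollment was selected on that reading. Attach the same caveat to any swab-versus-device comparison.
- If enrollment is complete, state the rule and the eye actually used.

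The cost is a short text change and one planned significance test that is either dropped or carries a caveat. Depending on how the sentences are reconciled, some patients who qualify under one reading might not be enrolled; the documents do not allow their number to be estimated.

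### Gland recovery after the 45-minute break is asserted, not shown; unequal carry-over would bias internal versus external by half the difference, and the planned order check has little power to reveal it

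*Combined protocol and SAP*

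**What the plan says.** The Protocol's account of visit two describes a two-period crossover within one day. "The patient is randomized to which application method, internal or external, is used first". "Between the first and second applications, there must be a waiting period of at least forty-five minutes". The reason given is: "This break ensures that the patient's tear glands have enough time to restore". The text adds that this recovery is needed if the device's effect is to be measured accurately. The outcome is one five-minute reading per application: "During both the first and second applications, Schirmer strips are used to measure tear production over the course of five minutes". No reading is described between the break and the second application.

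The Statistical Analysis Plan first compares internal and external stimulation with baseline. For those comparisons, "When making these comparisons, the order in which application method was used first will be factored in", and the stated purpose is: "This will help us determine whether or not the order of application methods impacts the final results". It later plans the head-to-head comparison: "We also plan to compare each application method to each other to determine if there is a statistically significant difference". There it names Sjogren's medication and baseline Schirmer category as factors to account for, but not order. It gives no model, period term or first-application analysis, and no rule for what follows if order turns out to matter.

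**The concern.** By the Protocol's own account, accurate measurement depends on gland recovery, yet recovery is neither supported by data nor observed. If the glands have not recovered, the second reading is too low. When the deficit depends on which method came first, the comparison of methods is distorted: the method that depletes more looks better than it is, because the other method is measured on depleted glands in half the patients.

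Two sets of planned results are exposed: the internal-versus-external difference, and each method's estimated mean change from baseline. A non-significant order check could be taken as evidence that the break worked, and with few patients it would be weak evidence.

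**Working it through.** **Inputs from the documents.** Two methods, randomized order, one Schirmer reading per application, a break of at least 45 minutes, and order factored into the baseline comparisons.

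**Not in the documents, so assumed.** Allocation 1:1 unless stated; deficits of 1 to 4 mm (4 mm is borrowed from the screening response threshold only to give a scale); 20 to 60 patients; SD 5 mm; within-patient correlation 0.5. The plan gives no sample size, power or SD, so there is no figure of its own to reproduce.

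**1. Expected readings.** Let T be the true internal-minus-external difference and P the effect of being second. Let cI be the change that a preceding internal application leaves in the external reading, and cE the reverse. Deficits are negative.

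- Internal first: internal minus external = T − P − cI
- External first: internal minus external = T + P + cE
- Average of the two orders = T + (cE − cI)/2

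P cancels; unequal carry-over does not. This average is also the period-adjusted estimate, so a period term leaves the bias in place. With T = 0:

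| cI, cE (mm) | Bias in internal − external (mm) |
|---|---|
| −2, −2 | 0.0 |
| −2, 0 | +1.0 |
| −3, −1 | +1.0 |
| −4, 0 | +2.0 |
| 0, −4 | −2.0 |

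A simulation of 40,000 trials of 40 patients gave +2.01 mm for the (−4, 0) case.

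**2. Mean change from baseline.** Half the patients receive a given method second, so its all-readings mean shifts by half of P plus the relevant carry-over. With P = 0 and both carry-overs −2 mm, each method's mean falls by 2/2 = 1.0 mm.

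**3. What the order check can see.** Second minus first is P + cE for internal and P + cI for external.

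- P = −2 with no carry-over: (−2, −2)
- Equal carry-over of −2 with P = 0: (−2, −2), the same pattern
- Carry-over of −4 after internal only: (0, −4)

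The difference between the two order effects is cE − cI, free of P. It is the quantity that causes the bias, and it can be estimated.

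**4. How well it can be estimated.** The contrast is between patients, on each patient's sum of two readings. SD of the sum = 5 × √(2 × 1.5) = 8.66 mm. SE = 8.66 × √(2/n), with n patients per order. For a true 4 mm difference, two-sided 5% t-test:

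| Patients | SE (mm) | 4/SE | Power |
|---|---|---|---|
| 20 | 3.87 | 1.03 | 16.5% |
| 40 | 2.74 | 1.46 | 29.6% |
| 60 | 2.24 | 1.79 | 42.1% |

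Letting SD range from 5 to 8 mm and correlation from 0.3 to 0.7 gives 9% to 49% (normal approximation). At 40 patients, the head-to-head SE is ½ × 5 × √(2 × 0.5) × √(2/20) = 0.79 mm. The spurious 2.0 mm is then 2.53 SEs, and the test of methods rejects in about 70% of trials although T = 0. The bias is therefore much more likely to produce a significant result than to be detected.

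**5. First applications only.** Internal-first minus external-first readings have expectation T whatever cI and cE are. At 40 patients the SE is 5 × √(2/20) = 1.58 mm, twice the 0.79 mm above.

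**6. Order left out of the head-to-head.** With a share p given internal first and no period term, a period effect contributes (1 − 2p) × P. For P = −2 mm this is 0.4 mm at 60:40 and 0.8 mm at 70:30; it is zero at 1:1 or with a period term.

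**The case against.** The best defence is that the design already does much of what is needed. Order is randomized, and the SAP factors it into both methods' baseline comparisons. If that means reporting results by order, each method's first-application change would already appear. The text is too brief to settle this.

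The defence also disposes of several stronger readings that a reader might infer:

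- *That the order check cannot tell carry-over from a harmless period effect.* This is true within one method. But order enters both baseline comparisons, and the difference between the two order effects isolates unequal carry-over. Only the common part is inseparable from period, and that part cancels from the head-to-head at 1:1 or with a period term. The limitation is precision, together with confounding by any method-by-period interaction.
- *That any depletion biases internal versus external.* Equal depletion does not. Nothing in the documents shows that depletion differs by method, or in which direction.
- *That the SAP pools first and second applications.* It does not say so. Order is simply not named for the head-to-head, and no restriction to first applications is stated.

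What remains is that recovery is unsupported, no contrast of order effects is specified, and such a contrast would be weak at modest sample sizes.

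**Conclusion.** The point holds as a conditional one. If carry-over differs by method, internal versus external is biased by half the difference whether or not order or period is adjusted for. If carry-over is equal, only the mean changes from baseline suffer, by half the deficit at 1:1 when both applications are used. The documents do not show that either occurs; they leave both possible and plan no robust estimate beside the exposed ones. The algebra needs no assumption about SD or sample size. The millimetre figures rest on assumed deficits, and the power figures on assumed sample size, SD and correlation. A reassuring order check should not be taken as confirmation that the glands recovered. This is an inexpensive improvement to the SAP, not evidence that the trial's results are wrong.

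**What to change.** In the SAP, commit to reporting the following beside the crossover results in every case, not conditional on a carry-over test:

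- (a) each method's mean change from baseline, with its confidence interval, from first applications only;
- (b) internal versus external from first applications only, with its confidence interval.

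Label both as supporting estimates. Also name order and period as terms in the internal-versus-external comparison; this protects against a period effect under unequal allocation, though not against unequal carry-over.

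Do not turn (b) into a rule that superiority may be claimed whenever its sign agrees with the crossover estimate. With equal methods and a 4 mm deficit after internal only, that rule would still pass a false conclusion in about 42% of trials at 40 patients (27% at 20, 48% at 60; same SD and correlation). The size and interval of (b) should be read, not just its sign.

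The cost is a few lines of analysis on data already collected. The downside is precision: each estimate uses about half the readings, and (b) is between patients, with an interval about twice as wide under the assumptions above.

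### Each device mode is tested against the visit-one Schirmer that also decides entry, so its mean change and p-value include any regression to the mean and between-visit drift

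*Combined protocol and SAP*

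**What the plan says.** The Protocol section describes one unstimulated tear measurement: a five-minute Schirmer under anesthesia on the screening day. That reading decides entry: "The patient must produce ten millimeters or less in at least one eye to qualify for the study". It is also the reference for the cotton-swab step, in which the patient swirls the swabs "until they produce four millimeters above their baseline in at least one eye". A further entry sentence follows: "In order to qualify for the study, the patient must produce four millimeters or greater in the study eye". The study eye is not defined.

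The device is used later: "After visit one, visit two can be completed the following day or any day during the next forty-five days". The purpose of that visit is stated plainly: "During visit two, the effectiveness of the device is tested". On allocation: "The patient is randomized to which application method, internal or external, is used first". On measurement: "During both the first and second applications, Schirmer strips are used to measure tear production over the course of five minutes". Both visit-two readings are taken with stimulation; no unstimulated or sham strip is described.

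The SAP section opens its analyses with: "First, we will look to compare both the internal and external stimulation results to the baseline results". It takes the order of the two modes into account. It then plans a significance test and a mean change against baseline for the swabs and for each mode, and a comparison of the methods with one another. It mentions no repeat baseline and no allowance for regression to the mean.

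**The concern.** A reading used to admit patients because it is low lies, on average, below those patients' usual level whenever it carries measurement error. A second reading then tends to rise even if nothing was done. Any general shift in unstimulated tearing between the visits adds to the same difference. With no unstimulated reading at visit two, neither part can be estimated or subtracted. Order of application is a visit-two factor, so adjusting for it reaches neither.

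This matters because the comparison with baseline is the only planned analysis that sets either device mode against no stimulation. A positive result could be reported as efficacy when part of it comes from selection or drift. More patients would not help: the bias stays the same while the standard error falls.

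**Working it through.** **What the documents supply.** The 10 mm entry limit, the 1-to-45-day gap, the two stimulated readings at visit two and randomization of order only. They give no mean, SD, repeatability, sample size, significance level, named test or study-eye rule, so there is no planned figure to reproduce. What follows is an illustration.

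**Assumptions.** Inert device, no drift, true tear level mean 6 and SD 4 mm, reading-error SD 3 mm, 20 patients, and a paired t-test at two-sided 5%, so that 2.5% of trials should favour the device by chance.

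**Hand check, one eye held to 10 mm or less, normal model.**
- Observed SD = √(4² + 3²) = 5 mm; repeatability r = 16/25 = 0.64.
- c = (10 − 6)/5 = 0.8; λ = φ(c)/Φ(c) = 0.2897/0.7881 = 0.3676.
- Expected rise = (1 − r) × SD × λ = 0.36 × 5 × 0.3676 = 0.66 mm.
- Variance of the selected baseline = 25 × (1 − 0.8 × 0.3676 − 0.3676²) = 14.27.
- Variance of the change = 0.36² × 14.27 + 25 × (1 − 0.64²) = 1.85 + 14.76 = 16.61; SD 4.08 mm.
- Noncentrality = 0.66/(4.08/√20) = 0.73. The noncentral t (19 df) then gives about 10% of trials favouring the device.

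**Simulation.** Schirmer values cannot be negative, so the calculation was repeated with a gamma-distributed true level, readings cut at 0 and, for the two-eye cases, a correlation of 0.7 between the eyes' true levels with independent reading errors.

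| Eye analysed | Spurious mean rise | Trials favouring an inert device (nominal 2.5%) |
|---|---|---|
| Arbitrary eye, either-eye entry rule | about +0.1 mm | 3% to 4% |
| The eye held to 10 mm or less | about +0.5 mm | 8% |
| Lower eye, either-eye entry rule | about +1.5 mm | 43% |
| Visit-two unstimulated comparator | 0.0 mm | 2% to 3% |

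The second row is the hand-checked case; the skewed distribution and the floor at 0 bring 0.66 mm down to about 0.5 mm. The last row holds by construction, because no drift within visit two was assumed.

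**Drift.** In the second-row setting, a group-wide shift of +1 mm between visits gives +1.4 mm and 36%; a shift of −1 mm gives −0.3 mm and 1%. The shift passes almost fully into the estimated change.

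**Swab rule.** The two 4 mm sentences can be read as a rise or as a total. With the same mean and SDs, a required rise that not every patient reaches gives +0.6 to +2.0 mm, for assumed swab effects of 10 down to 3 mm. A required total can turn the bias slightly negative in a drier population: −0.28 mm at mean 3 and SD 2 mm, a 3 mm swab effect, error SD 3 mm and half of the same-day error variance shared.

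**The contrast between modes.** Internal minus external uses two visit-two readings in randomized order. The screening value does not enter, so this bias does not either.

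**The case against.** The strongest reply is that the problem may be small. Under the either-eye rule with an arbitrary study eye, the illustration gives about 0.1 mm and hardly any inflation. The Protocol's own swab target is a 4 mm rise, and a device change of that order would not be produced by such a bias. The larger figures need inputs that the documents do not contain. No sentence makes the lower eye the study eye. Nothing suggests a group-wide drift, and random drift within patients adds noise, not bias. Because patients swirl until they reach the target, the swab rule may select only weakly. The added strip would also be imperfect: it always comes first and is no sham.

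All of this stands as a limit on size. A reader might infer that no change from baseline, however large, could be credited to the device, or that a false-positive rate near 43% is to be expected. The documents support neither. The first ignores how far a large change would exceed the plausible bias; the second depends on an eye rule that nobody has written down.

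It does not remove the point. The comparator is the entry reading, and the design yields no data from which the bias could be estimated. Its unknown size is a reason to limit the claim.

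**Conclusion.** The concern holds for the two device-versus-baseline comparisons and should be fixed. That the comparator is the entry reading, with no visit-two counterpart, follows directly from the text. The size does not: the illustrative +0.1, +0.5 and +1.5 mm rest on an assumed mean, SDs, between-eye correlation and sample size, and on which eye is analysed. The bias is probably upward, but it could be negligible and, under one reading of the swab rule, slightly negative.

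A small change from baseline therefore cannot be attributed to the device. A change well above the illustrated range would not be explained by regression to the mean alone, although the design could still not exclude drift.

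A reader might also infer that the whole trial is compromised. It is not: the randomized contrast between modes is untouched. A difference there would show that the two modes are not both inert, but not which of them beats no stimulation.

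**What to change.** 1. **Wording, no visit time.** State in the SAP that change from the screening Schirmer is uncontrolled and open to regression to the mean and between-visit drift, that its p-value will not by itself be reported as evidence of efficacy, and that causal conclusions rest on the randomized internal-versus-external contrast. Fix the study-eye rule before analysis, because the bias depends on it.

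2. **If visits remain to be run.** Take one unstimulated five-minute Schirmer at visit two before the first application, under the same anesthetic condition as the device readings; the Protocol states that condition only for screening, so it should be stated for visit two as well. Use this reading as the comparator for both modes and keep the screening value for eligibility only. If the Protocol's 45-minute rest is applied after it, the cost is 5 + 45 = 50 minutes at an existing visit. The SAP should say that this is not a sham control and that a test always taken first stays confounded with sequence.

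The two 4 mm swab sentences should be reconciled as a separate point of clarity.
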